### Planned Analysis

- a) Table: summarize proportion and two-sided 90% confidence interval around the observed SVR12 proportion using the Blyth-Still-Casella(BSC) method for binomial outcomes (HCVRNALDMS)
- b) Table: summarize proportion and two-sided 90% confidence interval around the observed SVR12 proportion of participants who are evaluable for SVR12 but exclude participants who prematurely discontinue study treatment for nonvirologic reasons (Completer Analysis) using the Blyth-Still-Casella(BSC) method for binomial outcomes (HCVRNALDMS)

## **8.2 Safety Outcome [IP]**

Note: For clarity of presentation, results for the primary safety outcome and for the secondary safety outcomes will be presented together in the analysis report.

### Primary Outcome Measure (from protocol section 9.2.1.2)

Occurrence of a Grade  $\geq 2$  AE (diagnosis, sign, symptom, or laboratory abnormality), SAE according to ICH criteria, or treatment-limiting AE (i.e., an AE reported as the reason for permanent discontinuation of study treatment).

Any event occurring after initiation of study treatment through to 28 days after date of last dose of study treatment will be included (except that an event that is ongoing at the same grade from before start of study treatment will be excluded).

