## 1 Introduction

This document describes the content proposed for the primary statistical analysis of ACTG A5327. The focus of this analysis will address the primary safety and efficacy objectives for Cohort 2 (8 weeks of treatment) as well as the secondary objectives for which data will be available at the time of the primary analysis. Details about analyses for review by the Study Monitoring Committee (SMC) are not included in this SAP as all participants had completed study treatment by the time of preparation of this SAP and no further reviews of the study by the SMC were to be undertaken.

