#### SAMPLE SIZE

A minimum of 44 participants will be enrolled in Cohort 1 and Cohort 2.

Cohort 1: Minimum of 17 participants will be enrolled.

Cohort 2: Minimum of 27 participants will be enrolled.

If a participant is discontinued from study treatment for non-virologic reasons or is not evaluable for SVR12 while enrollment is ongoing to the same cohort, then an additional participant may be enrolled to that cohort to help ensure that an adequate number complete study treatment and are evaluable for SVR12, up to a maximum enrollment of 50 participants.

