## 2.7 General Statistical Considerations

Key analysis decisions:

- Throughout, study entry is defined at the date of entry visit as recorded as the header date on the ADM0010.

- The analyzed measurement will, in general, be the measurement closest to the scheduled evaluation time, and the acceptable windows will be based on time since first study treatment dose.
- Data summaries and analyses will be presented for Cohort 2 only (the analysis of data for participants in Cohort 1 are included in a separate report).

Notes for conventions used in the primary analysis report:

- For the primary analysis report:
  - Lists will be sorted by variables in the order given with study participants identified using an alternate patient identifier (PubID, i.e. not ACTG patid).
  - Participant-specific dates will not be shown, but converted to time since start of study treatment (all participants did start study treatment).
- Each Table/Figure/Listing will be annotated with the name and location of the program used to create it.
- Validation:
  - Tables/figures requiring SDAC validation of the program used to generate the results will be flagged with “[V]”.
  - Tables/figures requiring independent programming of results by the SDAC validator will be flagged with “[IP]”.

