Note: Baseline is defined as the closest value on/before date of start of study treatment.

- ii. Baseline CD4+ cell count (/mm^3) (LBW0054): N, median, 1st and 3rd quartile, minimum and maximum;  
Note: Baseline is defined as the arithmetic mean of screening and entry values or, in the absence of one value, the one available.
  - iii. Baseline CD4+ cell percent (LBW0054): N, median, 1st and 3rd quartile, minimum and maximum;  
Note: Baseline is defined as the arithmetic mean of screening and entry values or, in the absence of one value, the one available.
- d) Table summarizing HIV-1 antiretroviral therapy (ARVs)
- i. Receiving HIV ARVs prior to entry (ANSTAB): number (%) yes and no
  - ii. HIV ARV regimen at entry (TXT0004): number (%) on each regimen
  - iii. HIV ARV regimen of interest for renal functions (TXT0004): number (%) on TDF + boosted PI, COBI, and other ARV regimens
  - iv. NNRTIs (TXT0004): number (%) on efavirenz, rilpivirine, tenfovir, and abacavir based regimens
  - v. Integrase Inhibitors (IIs) (TXT0004): number (%) on raltegravir and dolutegravir based regimens
  - vi. Protease Inhibitors (PIs) (TXT0004): number (%) on boosted PI based regimens
- e) Table summarizing baseline laboratory evaluations
- For each laboratory evaluation the following will be presented unless otherwise specified: N, median, 1st and 3rd quartile, minimum and maximum. If the lab value is graded, DAIDS grading scale will also be presented.
- Note: Baseline is defined as the last available value on or before the date of starting study treatment. Fasting per protocol is defined as nothing to eat or drink except prescription medications and water for at least 8 hours prior to the procedure. If nonfasting at the screening visit, the participant should return within 7 days for fasting blood draw. These panels are performed at the designated testing laboratory; see A5237 lab processing chart [LPC] for directions.
- i. Hematology characteristics (F2850): hematocrit, hemoglobin (g/dL), platelets (cells/mm^3), red blood cell (RBC) count, white blood cell (RBC) count (cells/mm^3), WBC differentials (absolute and percentage: lymphocytes, monocytes, neutrophils, eosinophils, basophils, reticulocyte count) and mean corpuscular volume (MCV).

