### Planned Analysis

- a) Table: summarize proportion and two-sided 90% confidence interval around the proportion of participants who have one of the defined AEs (EVW0206, EVW0207)
- b) Table: list of all events meeting the primary safety outcome definition (including weeks from start of study treatment, type of AE, grade, whether or not an SAE, whether or not it was a treatment limiting AE)

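### Read literally, the primary safety outcome counts a pre-existing Grade 3 or 4 event that improves to a lower grade still ≥2, but not one that stays at Grade 4

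*SAP*

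**What the plan says.** SAP Section 8.2 defines the primary safety outcome as a Grade ≥2 diagnosis, sign, symptom or laboratory abnormality, an SAE, or a treatment-limiting adverse event. The window runs from initiation of treatment to 28 days after the last dose. There is one exception for pre-existing events: "except that an event that is ongoing at the same grade from before start of study treatment will be excluded". The definition is attributed to protocol section 9.2.1.2.

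Planned analysis (a) in 8.2 is the proportion of participants with such an event and a two-sided 90% confidence interval. Planned analysis (b) is a listing, "including weeks from start of study treatment, type of AE, grade, whether or not an SAE" and whether the event was treatment-limiting. Pre-treatment grade is not among the items named.

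Section 9.5 takes over the same definition for events by type. Section 8.2 and the primsafe dataset in Section 10 carry the [IP] flag, which Section 2.7 explains: "Tables/figures requiring independent programming of results by the SDAC validator will be flagged with" that mark.

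Section 5(e) already plans a grade for baseline laboratory values: "If the lab value is graded, DAIDS grading scale will also be presented". It also fixes the reference value: "Baseline is defined as the last available value on or before the date of starting study treatment".

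**The concern.** The exception turns on equality of grade, not on whether the event is new or worse. Equality removes an unchanged event, as it should, but it leaves in an event that has become milder without falling below Grade 2. A participant whose pre-existing abnormality improves can then score as a primary safety failure while a participant unchanged at Grade 4 does not. That ordering is hard to defend for a safety outcome.

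Laboratory abnormalities are part of the outcome, and ALT and AST are among the chemistry values in Section 5(e). It is plausible that liver enzymes in acute HCV start high and pass down through the grades on treatment. The SAP gives no frequency for this, so it is an assumption.

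Independent programming does not settle the matter. If the two programmers read the exception differently, the SAP has no rule to decide between them. If both read it literally, no discrepancy appears. The 8.2(b) listing, as its contents are named, does not ensure that a reader could tell an improvement from a worsening.

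**Working it through.** The SAP states no figure on this point, so there is none to reproduce. The check is an enumeration of the rule and a scale for its effect.

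**1. Which transitions differ.** Take four levels: below 2, 2, 3 and 4. With one pre-treatment and one on-treatment level there are 4 × 4 = 16 paths. Compare the literal rule (a Grade ≥2 record counts unless its grade equals the pre-treatment grade) with a same-or-lower exclusion (it counts only if its grade exceeds the pre-treatment grade). This is for events that are neither SAEs nor treatment-limiting.

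| Pre-treatment → on treatment | Literal 8.2 | Same-or-lower exclusion |
|---|---|---|
| 2→2, 3→3, 4→4 | excluded | excluded |
| 3→2, 4→2, 4→3 | **counted** | **excluded** |
| any rise to Grade ≥2 | counted | counted |
| any level → below 2 | not counted | not counted |

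The rules differ in exactly three paths. All three start at Grade 3 or 4, and in all three the literal rule is the one that counts. The discrepancy therefore runs in one direction only, and only participants with a pre-treatment Grade 3 or 4 event can be affected.

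**2. Events whose grade changes more than once.** With two successive on-treatment records there are 4³ = 64 paths. Four paths fall and then rise again while staying at Grade ≥2 and no higher than the pre-treatment grade: 3→2→3, 4→2→3, 4→2→4 and 4→3→4. The literal rule counts them. A blanket same-or-lower exclusion would remove them, although the grade rose on treatment. If events that rise on treatment are left to the present text, the rules differ in 10 of the 64 paths. In each of the 10 the grade never rises and the literal rule counts. The total is 10 whether or not a fall below Grade 2 is taken to end the event, and no path moves in the opposite direction.

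**3. Effect on the proportion.** Inputs from the sample-size part of Section 2.1: "Cohort 2: Minimum of 27 participants will be enrolled", a Cohort 1 minimum of 17, and the provision "up to a maximum enrollment of 50 participants".

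- Planned minimum: n = 27, so one participant is 1/27 = 3.70 percentage points.
- Largest Cohort 2, if Cohort 1 has its minimum: 50 − 17 = 33, so one participant is 1/33 = 3.03 points.

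**4. Effect on the interval.** Section 8.2 names no interval method; exact Clopper-Pearson 90% limits are assumed here. Moving from k to k + 1 events, over all k:

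- n = 27: a limit moves by 0.19 to 5.90 points. The largest step is in the upper limit, from 10.5% at 0/27 to 16.4% at 1/27.
- n = 33: a limit moves by 0.16 to 4.91 points. The upper limit goes from 8.7% at 0/33 to 13.6% at 1/33.

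As an illustration with an assumed count, 8/27 = 29.6% (90% CI 15.7 to 47.1). One further participant who qualifies only through an improvement makes it 9/27 = 33.3% (18.6 to 50.9).

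**The case against.** The strongest reply is that 8.2 concerns events that occur after treatment starts, and an abnormality that was already present and is getting better does not naturally occur on treatment. On that view the exception is only a clarification that an unchanged abnormality, measured again, is not a new event. The reading is possible. But if ongoing events were out of scope from the start, the exception would be largely redundant; its presence suggests that ongoing events are in scope and that only those at an unchanged grade are taken out. The probable intent is new or worsened events, but no passage says so.

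A second reply is that much depends on sources not shown. Protocol section 9.2.1.2 may word the rule differently, entry criteria may limit severe pre-treatment events, and the SAP does not say whether a falling grade creates a record in EVW0206 or EVW0207. This stands, and it is why the number affected cannot be given.

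A third is that the consequence is small: a descriptive proportion, a listing of every qualifying event, and an error in the cautious direction. This also stands as a limit on weight. It does not remove the gap from a primary outcome definition, and the listing as named lacks the one item needed to spot the problem.

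A reader might infer that the reported safety rate will be inflated, or that a safety conclusion would change. The SAP supports neither. It does not show that any participant has such an event or that the programmers will read the rule literally, and 8.2 has no threshold or comparison.

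**Conclusion.** The point holds as a defect in the wording of a primary outcome. As written, 8.2 counts 3→2, 4→2 and 4→3 and excludes 4→4, and nothing else in the SAP corrects this. The effect can only be upward: 3.7 points per participant at n = 27, or 3.0 points at n = 33, and only for a participant with no other qualifying event in the window. The total cannot exceed the number with a pre-treatment Grade 3 or 4 event, and it may be zero. For laboratory values, the grades planned in Section 5(e) would show that ceiling.

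The conclusion rests on the literal reading, which is the better supported but not the only one. The interval figures also rest on the assumed Clopper-Pearson method. It is worth fixing because the remedy is short, not because a formal decision depends on it.

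**What to change.** In Section 8.2, reword the exception so that it excludes an event *ongoing at the same or a lower grade than before start of study treatment*, and add:

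- **Reference grade.** For laboratory values, the grade of the last value on or before first dose (the Section 5(e) rule). For diagnoses, signs and symptoms, the grade ongoing at first dose.
- **Limits of the addition.** The lower-grade exclusion does not apply to an SAE, a treatment-limiting adverse event, or an event whose grade rises on treatment. These stay as the present text handles them.
- **Listing.** Add pre-treatment grade to the 8.2(b) listing.
- **Scope.** Apply the rule to 8.2(a) and (b), 9.5(a) and primsafe.

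The definition is attributed to the protocol, and Section 1 records that "all participants had completed study treatment by the time of preparation of this SAP". The change should therefore be dated and justified, and the as-written proportion with its 90% interval reported alongside. If nobody is affected, the two proportions agree and the question is closed.

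The cost is a small change to a derivation that is programmed twice, one extra table row and one extra listing column. No new data collection is needed, and laboratory baseline grades are already planned. The drawback is a late change to a primary outcome in an open-label trial, one that can only lower the count; reporting both versions makes it visible.

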## 6 Study status and loss to follow up [V]

Purpose: To summarize extent of follow-up on study.

- a) CONSORT diagram: number of participants enrolled, number who started treatment, completed treatment, and completed study
- b) Table: On study treatment number (%) by category (F4003 and F1601)  
Categories included are:
  - i. Completed planned treatment period and post treatment follow-up
  - ii. Completed planned treatment period but off study early
  - iii. Discontinued study treatment early and completed planned post treatment follow-up
  - iv. Discontinued study treatment early and discontinued post treatment follow-up early
- c) List: Reasons off study treatment early (include both the category and text field from F4003)
- d) List: Reasons off study early (include both the category and text field from F1601)

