### 9.5 AEs by type of event [V]

#### Secondary Outcome Measure (from protocol section 9.2.2.5)

Occurrence of the AEs detailed in section 9.2.1.2 of the protocol (Section 9.1 in this document) by type of event. Type of events include: diagnosis, sign, symptom, laboratory abnormality, SAE according to ICH criteria, or treatment-limiting AE. Additional analysis of selected renal safety parameters is included because of a concern that participants taking TDF might be at increased risk for such events.

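### The same-grade exception in the primary safety outcome also covers SAEs and treatment-limiting AEs, which do not depend on grade

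*SAP*

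**What the plan says.** SAP Section 8.2 (Primary Outcome Measure) defines the primary safety outcome by three alternatives. The first is a Grade ≥2 AE. The other two are "SAE according to ICH criteria, or treatment-limiting AE (i.e., an AE reported as the reason for permanent discontinuation of study treatment"). Neither of these carries a grade threshold.

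The next sentence sets the window: "Any event occurring after initiation of study treatment through to 28 days after date of last dose of study treatment will be included". A parenthesis then removes some events: "except that an event that is ongoing at the same grade from before start of study treatment will be excluded".

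Three outputs bear on the point:

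- Section 8.2 a) will "summarize proportion and two-sided 90% confidence interval around the proportion of participants who have one of the defined AEs".
- Section 8.2 b) is a "list of all events meeting the primary safety outcome definition", with columns for SAE and treatment-limiting status.
- Section 9.5 breaks events down by type, with SAE and treatment-limiting AE among the types, and starts from "Occurrence of the AEs detailed in section 9.2.1.2 of the protocol", the same protocol section under which 8.2 gives its definition.

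Separately, Section 6 c) plans a disposition output: "List: Reasons off study treatment early (include both the category and text field from F4003").

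**The concern.** Excluding an unchanged pre-existing abnormality makes sense for the Grade ≥2 criterion: if the grade has not moved, nothing new has happened on that criterion. The reasoning does not carry over to the other two. What is new there is the seriousness or the discontinuation, and a test of unchanged grade looks at neither. A condition present at, say, Grade 1 or 2 before the first dose can lead to hospitalisation or to permanent discontinuation while its recorded grade stays the same.

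Safety and tolerability is primary objective 2 (Section 2.3), and SAEs and treatment-limiting AEs bear most directly on it. On these two criteria the exception can only take events away, so any error runs in one direction. The report could also show an AE discontinuation in its disposition list that its primary safety analysis does not count.

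**Working it through.** The SAP gives no expected rate, power or sample-size figure for the safety outcome, so there is no stated figure to reproduce. The check is one of wording, followed by an illustration of scale.

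**Step 1: each criterion against the exception (Section 8.2).**

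| Criterion | What makes an event qualify | Does unchanged grade show that nothing new happened? |
|---|---|---|
| Grade ≥2 AE | Grade | Yes |
| SAE | ICH criteria | No |
| Treatment-limiting AE | Reported reason for permanent discontinuation | No |

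The exception follows directly on the phrase that brings in any event in the window, and its only test is unchanged grade. As written it reaches all three rows.

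**Step 2: whether another section restores the event.**

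- 8.2 a) counts participants with one of the defined AEs, so an excluded event does not contribute.
- 8.2 b) is limited to events meeting the definition, so an excluded SAE or treatment-limiting AE never reaches the columns meant to flag it.
- 9.5 refers back to the same protocol definition. Its planned list a) names its source datasets without repeating the restriction, so the omission is probable there, not certain.
- 6 c) would show why treatment stopped early. It is not a safety count, and it does not cover an SAE that did not end treatment.

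**Step 3: size.** Inputs: the minimum Cohort 2 enrolment is 27; the overall maximum is 50 and the Cohort 1 minimum is 17 (all Section 2.1). The number of affected participants is unknown.

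One participant whose only qualifying event is removed lowers the composite proportion by 1/27 = 3.7 percentage points. At the largest possible Cohort 2, 50 − 17 = 33, the figure is 1/33 = 3.0 points.

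Section 8.2 names no interval method. Assuming exact (Clopper-Pearson) two-sided 90% intervals at n = 27:

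- Upper limit for 0/27: 1 − 0.05^(1/27) = 10.5%.
- Upper limit for 1/27: the p that solves (1 − p)^27 + 27p(1 − p)^26 = 0.05, which is 16.4%.

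| Composite count with the event excluded | With the event counted |
|---|---|
| 0/27 = 0% (0 to 10.5) | 1/27 = 3.7% (0.2 to 16.4) |
| 5/27 = 18.5% (7.6 to 35.1) | 6/27 = 22.2% (10.1 to 39.2) |
| 13/27 = 48.1% (31.3 to 65.3) | 14/27 = 51.9% (34.7 to 68.7) |

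The counts are assumed, to show a range. The upper limit moves by 16.4 − 10.5 = 5.9 points in the first row, 39.2 − 35.1 = 4.1 in the second and 68.7 − 65.3 = 3.4 in the third.

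**The case against.** The best answer is that an event here means a qualifying occurrence, not the underlying condition. The SAP defines a treatment-limiting AE as one reported as the reason for stopping study treatment. That status cannot exist before the first dose, so it cannot be ongoing from before it. The same can be said of an AE that first meets SAE criteria on treatment. On this reading the exception already touches only the Grade ≥2 criterion.

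The reading is possible but strained. Only an underlying AE can be ongoing at the same grade; seriousness and discontinuation have no grade to keep. If this is what is meant, the text should say so. The outcome is marked for independent programming, and two programmers could both drop such an event, so that validation would not detect it, or could disagree.

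Other points stand and limit the weight of the concern:

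- A condition that becomes serious or ends treatment will often rise in grade too, and would then be counted.
- A participant with any other qualifying event remains in the composite proportion. Only the event-level outputs lose the entry.
- Discontinuations stay visible in Section 6 c).
- The definition is attributed to protocol section 9.2.1.2, which is not at hand and may carry or clarify the wording.

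A reader might infer that a reported treatment-limiting rate would fall from 1/27 to 0/27. The SAP does not support that: 8.2 a) plans one composite proportion and no proportion by criterion. The 0/27 against 1/27 comparison applies to the reported figure only if no other participant has any qualifying event, including any new Grade ≥2 laboratory abnormality.

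**Conclusion.** The point holds as a defect in the wording of a primary outcome. Read plainly, Section 8.2 excludes an SAE or treatment-limiting AE that arises from a pre-existing condition at unchanged grade, and no other section restores it as a safety count.

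The effect is probably small. It alters the primary proportion only when a participant has a pre-existing condition, that condition becomes serious or treatment-limiting within the window, its grade does not change, and the participant has no other qualifying event. Each such participant costs 3.7 points at n = 27. The interval limits above rest on an assumed method and assumed counts.

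A reader might go further and conclude that the safety result is biased, or that AE discontinuations are hidden. The SAP shows neither: bias depends on such cases occurring, and Section 6 c) lists reasons for stopping treatment early. What it does show is that any error on these two criteria would favour the regimen.

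**What to change.** Limit the exception in Section 8.2 to the Grade ≥2 criterion, for example:

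> An AE present before the first dose and continuing without a change of grade does not satisfy the Grade ≥2 criterion. If, after the first dose and within the window, it meets ICH SAE criteria or is reported as the reason for permanent discontinuation, it is counted whatever its pre-treatment grade.

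Apply the same rule in the primsafe dataset, listing 8.2 b) and Section 9.5, and check it against protocol section 9.2.1.2. If the protocol carries the present wording and it has to stand as the primary definition, a supplementary count and listing of the excluded SAEs and treatment-limiting AEs would make them visible.

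The programming cost is one condition in primsafe. The reported proportion may become slightly less favourable. Section 1 says that all participants had completed treatment when the SAP was prepared, and the study is open-label, so the change should be documented as a clarification made after treatment was completed. It concerns only which events are counted and implies nothing about when treatment should be stopped.
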